5 Statistical Methods and Determination of Sample Size.....	15
5.1 Statistical Methods.....	15
5.1.1 Hypotheses and Statistical Methods for Primary, Secondary, and Exploratory Objectives	15
5.1.1.1 Hypotheses.....	15
5.1.1.2 Statistical Methods	15
5.2 Interim / Preliminary Analysis	18
5.3 Determination of Sample Size and Power Calculation.....	19
5.4 Data Review for Statistical Purposes.....	19
5.5 Changes in the Conduct of the Study or Planned Analyses	20
6 References List	21
7 Statistical Analysis Plan TLF Shells - Main Outputs.....	Error! Bookmark not defined.

List of Tables.....	22
----------------------------	-----------

List of Abbreviations

CAP	Community-Acquired Pneumonia
COPD	Chronic Obstructive Pulmonary Disease
DxCG	Diagnostic Cost Groups
EMR	Electronic Medical Record
HA	Hemagglutinin
HAI	Hemagglutination Inhibition
ICD-10	International Classification of Diseases, 10th Revision
IRB	Institutional Review Board
KPNC	Kaiser Permanente Northern California
KPVSC	Kaiser Permanente Vaccine Study Center
LRTI	Lower Respiratory Tract Infection
PCR	Polymerase Chain Reaction
RSV	Respiratory Syncytial Virus
rHR	Relative Hazard Ratio
rVE	Relative Vaccine Effectiveness
SAP	Statistical Analysis Plan
SD-IIV	Standard-Dose Inactivated Influenza Vaccine
SD-IIV4	Standard-Dose Quadrivalent Inactivated Influenza Vaccine
VE	Vaccine Effectiveness

1 Introduction

Influenza is transmitted through inhalation of virus-containing droplets from infected individuals. The incubation period is usually 1 to 2 days. The virus multiplies in the ciliated columnar epithelium of the upper- and lower-respiratory tract, causing cellular necrosis and sloughing. Virus shedding typically begins just before illness onset (within 24 hours), rapidly peaks, and remains elevated for 1 to 2 days before rapidly declining to low levels. Usually, virus shedding lasts a total of 5 to 10 days.

There is considerable variation in the severity of illness in different individuals, partly due to age, general health, and immune status relative to previous influenza infections and vaccination. The classic symptoms include rapid onset (12 hours or less) of malaise, fever, myalgia, headache, and a non-productive cough or sore throat. Most symptoms last several days, but malaise and cough may last for a week or more. Complications of influenza include primary viral pneumonia, secondary bacterial pneumonia, and exacerbation of underlying medical conditions such as chronic obstructive pulmonary disease and congestive heart failure.

While influenza affects all age groups, seniors, children younger than 5 years of age, and persons with underlying health problems are at increased risk for complications. Members of high-risk groups who become ill with influenza are more likely than the general population to require hospitalization for complications of the infection (e.g., pneumonia and cardiovascular events). Groups considered at higher risk for influenza-related complications include persons aged ≥ 65 years due to immunosenescence and higher likelihood of chronic medical conditions that put them at increased risk for severe influenza illness, and persons 50–64 years of age and older (also more likely to have chronic medical conditions that put them at increased risk).

Vaccination with influenza vaccine is the primary method for preventing influenza and its severe complications. It has been shown to be effective in reducing influenza-associated morbidity and mortality in groups at increased risk for influenza-related complications such as infants and young children and persons 50 years of age and older. Of note, immune responses to the vaccine are lower in seniors than those in young healthy adults. Strategies to improve immune responses to the vaccine in the elderly population could provide significant additional reductions in influenza-associated morbidity and mortality. One approach is to increase the dose of hemagglutinin (HA) in vaccines. Previous studies evaluating the immune responses in terms of hemagglutination inhibition (HAI) antibodies with higher doses of HA per strain in different influenza vaccines support a dose-response effect.

Flublok Quadrivalent vaccine is a recombinant HA influenza vaccine indicated for active immunization against disease caused by influenza A subtype viruses and type B viruses contained in the vaccine for adults 18 years of age and older. Use of recombinant DNA techniques to produce vaccine antigen expressed in cell culture is a method that avoids growing the influenza viruses in embryonated hens' eggs. Recombinant technology also allows control over the sequence of the full-length HA produced. The recombinant proteins are highly purified and the vaccine contains no egg protein, preservatives, or antibiotics, any of which may produce hypersensitivity reaction in some individuals.

Flublok Quadrivalent vaccine contains 45 µg HA per virus strain per dose, 3 times the amount of HA compared to standard-dose inactivated quadrivalent influenza vaccine (SD-IIV4). The high purity of a recombinant antigen enables administration of a higher concentration of HA antigen without an increase in adverse effects in humans. This higher dose of antigen may be a particular advantage to older adults whose immune responses to influenza vaccines can be suboptimal.

During this study, Flublok Quadrivalent or SD-IIV will be administered according to the guidelines in the Prescribing Information materials and only to persons for whom it is indicated. The 2018–2019, 2019–2020, and 2020–2021 formulations of recombinant influenza vaccine (Flublok Quadrivalent vaccine) and SD-IIV will be evaluated as described below.

The overall objective of this study is to describe the effectiveness of Flublok Quadrivalent vaccine compared to SD-IIV in adults 18 through 64 years of age.

2 Study Objectives

2.1 Primary Objective

Among all adults 50–64 years who receive either Flublok Quadrivalent or SD-IIV during the 2018–2019, 2019–2020, and/or 2020–2021 influenza seasons, we will estimate the relative vaccine effectiveness (rVE) of Flublok Quadrivalent vaccine versus SD-IIV against the following outcome:

- All PCR-confirmed influenza.

2.2 Secondary Objectives

Among all adults 50–64 years who receive either Flublok Quadrivalent or SD-IIV during the 2018–2019, 2019–2020, and/or 2020–2021 influenza seasons, we will estimate the rVE of Flublok Quadrivalent vaccine versus SD-IIV against the following outcomes:

- PCR-confirmed hospitalized influenza
- Hospitalized community-acquired pneumonia (CAP) (we will only include primary diagnoses for this outcome)
- Hospitalized cardio-respiratory events combined (e.g., CAP, other lower respiratory tract infections [LRTI], acute myocardial infarction, congestive heart failure, stroke, atrial fibrillation) (we will only include primary diagnoses for this outcome)
- All PCR-confirmed influenza A
- All PCR-confirmed influenza B

For these 5 secondary objectives, adjustment for multiplicity will be applied.

Sub-analyses of *primary* outcome in sub-groups defined by pre-existing conditions (listed below) will also be conducted among adults 50–64 years. Additionally, sub-analyses of *secondary*

outcomes of sub-groups defined by pre-existing conditions will be conducted as feasible among adults 50–64 years.

“Pre-existing” will be defined as history of a condition in the 3 years prior to vaccination date.

- i. **Cardiovascular preexisting conditions composite, which may include:** myocardial infarction, cerebrovascular accident, atrial fibrillation, arrhythmias, coronary artery disease, valvular heart disease/valvuloplasty, chronic/congestive heart failure and/or congenital heart defects, CABG, angioplasty/stents, cardioversion, pacemaker, implantable cardioverter defibrillator, LVAD, heart transplant, hypertensive disease
- ii. **Respiratory preexisting conditions composite, which may include:** COPD and/or pulmonary HTN
- iii. **Cardiorespiratory preexisting conditions composite:** combined pre-existing conditions (a) and (b) above
- iv. **Obesity:** based on available height/weight data for a calculated BMI ≥ 30 or an obesity diagnosis (e.g., ICD-10 E66.9)
- v. **Diabetes:** based on a diagnosis of diabetes

2.3 Exploratory Objectives

- To estimate the rVE of Flublok Quadrivalent vaccine versus SD-IIV in vaccinees aged 50–64 years against the following exploratory outcomes if time allows, potentially including:
 - a. Diagnosed with influenza (includes [1] adults with a PCR-positive influenza and [2] adults clinically-diagnosed with influenza in any setting but not tested); this outcome will exclude those with a clinically-diagnosed influenza but are tested and PCR-negative)
 - b. All-cause hospitalizations (excluding pregnancy-related hospitalizations)
 - c. All-cause mortality
- To estimate the rVE of Flublok Quadrivalent vaccine versus SD-IIV in other age ranges of vaccinees—aged 18–64 years and aged 18–49 years—against the following outcomes, if time allows:
 - a. All PCR-confirmed influenza
 - b. All PCR-confirmed influenza A and influenza B (separate rVE estimates)
 - c. PCR-confirmed hospitalized influenza
 - d. Hospitalized CAP
 - e. Hospitalized cardio-respiratory events combined
 - f. All-cause hospitalization (excluding pregnancy-related hospitalizations)
 - g. All-cause mortality
- Sub-analyses of the primary and secondary outcomes of sub-groups defined by pre-existing conditions (as described above in Section 2.2) will be conducted among adults 18–49 years as feasible

- To estimate the rVE of Flublok Quadrivalent vaccine versus SD-IIV among adults aged 18–64 years for PCR-confirmed influenza A subtypes (A(H1N1)pdm09 and A(H3)) and lineage for type B influenza (B/Victoria, B/Yamagata) as feasible
- Other exploratory objectives may be developed, such as vaccination waning or changes in subtypes circulating during an influenza season

3 Description of the Overall Study Design and Plan

3.1 Study Design

To estimate the rVE of Flublok Quadrivalent vaccine versus SD-IIV against all PCR-confirmed influenza in vaccinees aged 18–64 years, this study will compare the incidence of PCR-confirmed influenza among Flublok Quadrivalent vaccinees versus SD-IIV vaccinees. Our primary comparison will be focused on adults aged 50–64 years at KPNC during the 2018–2019, 2019–2020, and 2020–2021 influenza seasons. We will also assess all adults aged 18–64 years for both influenza seasons.

3.2 Trial Plan

This study will employ a design whereby KPVC will ensure that all clinics in KPNC will receive alternating shipments of Flublok Quadrivalent vaccine or SD-IIV. All KPNC facilities will follow a schedule that alternates which vaccine is supplied to each influenza clinic throughout the 3-year study period.

We will block facilities and randomize within blocks (see protocol **Section 5.1.4**), ensuring that roughly half the facilities within each block initially administer Flublok Quadrivalent vaccine and the other half administer a SD-IIV. After the initial supply, the half that started with Flublok Quadrivalent vaccine will be supplied with a SD-IIV, and the half that started with a SD-IIV will be supplied with Flublok Quadrivalent vaccine (see **Figure 1**). The supply of each clinic will then alternate between the two vaccines; that is, Flublok Quadrivalent vaccine alternating with a SD-IIV with each delivery of vaccine to the clinics.

Figure 1: Visual of block randomization influenza vaccine administration schedule			
	Week 1	Week 2	Week 3
Block A			
Facility 1			
Facility 3			
Facility 5	Flublok	Comparator IIV	Flublok
Facility 7			
Facility 9			
Block B			
Facility 2			
Facility 4			
Facility 6	Comparator IIV	Flublok	Comparator IIV
Facility 8			
Facility 10			

Data Extraction

Pertinent data will be extracted from the KPNC databases to create study datasets in the required file format for analysis (e.g., Excel spreadsheets, SAS datasets). Databases from which data will be extracted include various encounters (inpatient, outpatient, hospitalizations, emergency department, etc.), laboratory tests, documentation of immunizations (e.g., influenza vaccination history), and clinical outcomes and diagnoses, as well as demographic and membership data.

The data analyst will perform validation of the study data throughout the data management process by utilizing the following types of checks as applicable:

- Internal consistency checks (e.g., data undergo range checks, including consistency of dates of birth with vaccination dates, checks for completeness and missing values, etc.)
- External data checks (e.g., data from one database may be compared with data from other databases)
- Error checks written for specific databases.

4 Endpoints and Assessment Methods

4.1 Primary Endpoints and Assessment Methods

Among all adults 50–64 years who receive either Flublok Quadrivalent or SD-IIV during the 2018–2019, 2019–2020, and/or 2020–2021 influenza seasons, we will estimate the relative vaccine effectiveness (rVE) of Flublok Quadrivalent vaccine versus SD-IIV against all PCR-confirmed influenza.

All microbiological testing is conducted at KPNC laboratories that have used real-time PCR tests for influenza since 2006. PCR results are categorized as positive for influenza A; positive for influenza B; or negative for both (PCR results are also categorized as

positive or negative for respiratory syncytial virus [RSV]). In the KPNC system, influenza PCR tests are used for clinical purposes, thus the "trigger" for an influenza PCR test is based on clinical presentation. The decision to test is up to each physician. KPNC monitors the influenza season which can affect the total amount of influenza testing in adults. Once the KPNC laboratories complete the PCR testing, the test result is updated in the patient's EMR.

Among adults aged 50–64 years who are vaccinated with Flublok or an SD-IIV, we plan to assess the number of adults who have a PCR-positive test ≥ 14 days after vaccination up through to the end of each influenza season (as determined by KPNC, which is generally when the proportion of influenza-positive PCR tests drops below 10%) or the first week of May, whichever is later, compared with those who do not have a PCR-positive test by vaccine received. To be included in the cohort for analysis, the PCR test must occur during the influenza season. The influenza season is defined as the first day that KPNC begins use of the Cepheid GeneXpert PCR assay for the influenza season (generally the first Tuesday of October); the end of the season is generally determined when the proportion of influenza-positive PCR tests drops below 10%, or the first week of May, whichever is later.

We will only count the first PCR positive test per patient in any single season.

4.2 Secondary Endpoints and Assessment Methods

For each of the secondary outcomes listed below, we will count the first event of the outcome per influenza season and censor follow-up after the first event. The influenza season is defined as the first day that KPNC begins use of the Cepheid GeneXpert PCR assay for the influenza season (generally the first Tuesday of October); the end of the season is generally determined when the proportion of influenza-positive PCR tests drops below 10%, or the first week of May, whichever is later.

For all secondary objectives excluding the sub-analyses by pre-existing conditions, adjustment for multiplicity will be applied following the Holm adjustment method¹:

1. We will rank order the 5 p-values obtained from tests of the 5 null hypotheses about rVE with respect to each of the 5 secondary outcomes listed above.
2. The 5 p-values will be ranked in order from the smallest p-value to the largest: $p_{(01)} \leq p_{(02)} \leq p_{(03)} \leq p_{(04)} \leq p_{(05)}$
3. The corresponding alpha critical values to determine significance are to be used based on rank:
 - i. $\alpha_{(C_01)} = \alpha/5 = 0.0100$
 - ii. $\alpha_{(C_02)} = \alpha/4 = 0.0125$
 - iii. $\alpha_{(C_03)} = \alpha/3 = 0.0167$
 - iv. $\alpha_{(C_04)} = \alpha/2 = 0.0250$
 - v. $\alpha_{(C_05)} = \alpha/1 = 0.0500$

The 5 hypothesis tests will be done sequentially in the order given above, until one of the p-values is found to be higher than the corresponding critical value. If the lowest p-value is below 0.01, we

will reject the corresponding null hypothesis, and proceed to the next-lowest p-value. If, and only if, both the 1st and 2nd p-values are below their corresponding critical values, we will proceed to the 3rd lowest p-value. We will test the 5 secondary hypotheses sequentially in this way, comparing the next p-value to its critical value only if all of the lower p-values were below their corresponding critical values.

[figure not shown]
Among all adults 50–64 years who receive either Flublok Quadrivalent or SD-IIV during the 2018–2019, 2019–2020, and/or 2020–2021 influenza seasons, we will estimate the rVE of Flublok Quadrivalent vaccine versus SD-IIV against the following outcomes:

- PCR-confirmed hospitalized influenza

Among adults aged 50–64 years who are vaccinated with Flublok or an SD-IIV, we plan to assess the number of adults who have a PCR-positive test during the influenza season ≥ 14 days after vaccination and are hospitalized.

The PCR-positive test must occur either: (1) during the hospital stay, or (2) a hospitalization that begins ≤ 14 days after the PCR-positive test. Visually (where the • represents a hospitalization and the PCR-positive result occurs on Day 0):

Figure 1: Timing of PCR-positive test relative to hospitalization outcome

- Hospitalized community-acquired pneumonia (CAP)

Among adults aged 50–64 years who are vaccinated with Flublok or an SD-IIV, we plan to assess the number of adults who were hospitalized with a diagnosis of community-acquired pneumonia (CAP) regardless of whether a PCR test was done.

The hospitalization for CAP must occur during the influenza season and no later than 14 days after the last day of the influenza season, as determined by KPNC.

To identify diagnoses of CAP, we will start with preliminary list of ICD-10 codes that has been previously used by KPNC (**Table 1**). Case ascertainment of CAP may be refined using an iterative process during the data analysis stage.

- Hospitalized cardio-respiratory events combined (e.g., CAP, other lower respiratory tract infections [LRTI], acute myocardial infarction, congestive heart failure, stroke)

Among adults aged 50–64 years who are vaccinated with Flublok or an SD-IIV, we plan to assess the number of adults who were hospitalized with a diagnosis of a cardio-respiratory event regardless of whether a PCR test was done.

The hospitalization for a cardio-respiratory event must occur during the influenza season and no later than 14 days after the last day of the influenza season, as determined by KPNC. To identify diagnoses of a cardio-respiratory event, we will start with preliminary list of ICD-10 codes that has been previously used by KPNC (**Table 1**).

- All PCR-confirmed influenza A

Among adults aged 50–64 years who are vaccinated with Flublok or an SD-IIV, we plan to assess the number of adults who have influenza A as identified by a PCR-positive test ≥ 14 days after vaccination up through to the end of each influenza season, compared with those who do not have a PCR-positive test by vaccine received. To be included in the cohort for analysis, the PCR test must occur during the influenza season.

- All PCR-confirmed influenza B

Among adults aged 50–64 years who are vaccinated with Flublok or an SD-IIV, we plan to assess the number of adults who have influenza B as identified by a PCR-positive test ≥ 14 days after vaccination up through to the end of each influenza season, compared with those who do not have a PCR-positive test by vaccine received. To be included in the cohort for analysis, the PCR test must occur during the influenza season.

- Sub-analyses by pre-existing conditions

“Pre-existing” will be defined as history of a condition as identified using ICD-10 codes in the 3 years prior to vaccination date.

- i. **Cardiovascular preexisting conditions composite, which may include:** myocardial infarction, cerebrovascular accident, atrial fibrillation, arrhythmias, coronary artery disease, valvular heart disease/valvuloplasty, chronic/congestive heart failure and/or congenital heart defects, CABG, angioplasty/stents, cardioversion, pacemaker, implantable cardioverter defibrillator, LVAD, heart transplant, hypertensive disease
- ii. **Respiratory preexisting conditions composite, which may include:** COPD and/or pulmonary HTN
- iii. **Cardiorespiratory preexisting conditions composite:** combined pre-existing conditions (a) and (b) above
- iv. **Obesity:** based on available height/weight data for a calculated BMI ≥ 30 or an obesity diagnosis (e.g., ICD-10 E66.9)

- v. **Diabetes:** based on a diagnosis of diabetes

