We will also be monitoring the balance of potential confounders that may be related to influenza and to PCR testing in order to confirm that we are achieving the balance intended by our quasi-randomized shipment of vaccines to clinics. Once vaccinations begin, we will monitor on a weekly basis the balance of Flublok vaccinees versus SD-IIV vaccinees with respect to facility, sex, and age group (18–49 years and 50–64 years). Additional demographic variables such as race and ethnicity may also be monitored. We will also monitor balance with respect to comorbidities such as chronic obstructive pulmonary disease (COPD), asthma, and diabetes (to be specified further in the SAP). If we find that any facility is using Flublok or SD-IIV more (or less) than needed to achieve balance, we will work with the influenza program manager to adjust what is being administered. If despite our efforts, there is still imbalance, we can address these imbalances at the analysis stage, adjusting for, or stratifying by, the relevant covariates.

We plan to assess the outcomes that occur ≥ 14 days after vaccination up through April 30 of each influenza season. It is possible that patients enter, exit, and re-enter the KPNC population during the study period. At the analysis stage, we will make the most appropriate determination for how to handle such cases.

For outcomes not based on PCR-confirmed influenza (e.g., hospitalized pneumonia and cardio-respiratory events), we will develop an algorithm (to be described in the Statistical Analysis Plan) to measure the intensity of influenza circulation to guide when to start and stop following for such events (e.g., as determined by the algorithm, hospitalized pneumonia during June when influenza is not circulating would not be included).

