24	680,301	680,301	0.00065	0.95	0.05	0.12

Power of 3-yr study comparing FluBlok v Comparators
Power to detect relative VE against 5 types of outcome events
By age group (or chronic disease status) and outcome
2-sided alpha=0.05 (likelihood ratio chi-sq test for superiority)
800,000 vaccinees expected per yr: 400K fluBlok v. 400K comparators

age=50-64 outcome=flu, test+

row	N expectd 3 yrs FluBlok	N expectd 3 yrs Comprtr	proportion of comparators who have the outcome	RR = 1 minus relative VE	Relative VE: % of breakthru cases prevented	Power (prob. of rejecting Ho if rel_VE is true)
25	519,699	519,699	0.00205	0.70	0.30	>.99
26	519,699	519,699	0.00205	0.75	0.25	>.99
27	519,699	519,699	0.00205	0.80	0.20	>.99
28	519,699	519,699	0.00205	0.85	0.15	0.95
29	519,699	519,699	0.00205	0.90	0.10	0.66
30	519,699	519,699	0.00205	0.95	0.05	0.22

age=50-64 outcome=hosp, flutest+

row	N expectd 3 yrs FluBlok	N expectd 3 yrs Comprtr	proportion of comparators who have the outcome	RR = 1 minus relative VE	Relative VE: % of breakthru cases prevented	Power (prob. of rejecting Ho if rel_VE is true)
31	519,699	519,699	0.00120	0.70	0.30	>.99
32	519,699	519,699	0.00120	0.75	0.25	>.99
33	519,699	519,699	0.00120	0.80	0.20	0.96
34	519,699	519,699	0.00120	0.85	0.15	0.79
35	519,699	519,699	0.00120	0.90	0.10	0.44
36	519,699	519,699	0.00120	0.95	0.05	0.15

age=50-64 outcome=PneumoniaHosp,Dec-March

row	N expectd 3 yrs FluBlok	N expectd 3 yrs Comprtr	proportion of comparators who have the outcome	RR = 1 minus relative VE	Relative VE: % of breakthru cases prevented	Power (prob. of rejecting Ho if rel_VE is true)
37	519,699	519,699	0.00248	0.70	0.30	>.99
38	519,699	519,699	0.00248	0.75	0.25	>.99
39	519,699	519,699	0.00248	0.80	0.20	>.99
40	519,699	519,699	0.00248	0.85	0.15	0.98
41	519,699	519,699	0.00248	0.90	0.10	0.74
42	519,699	519,699	0.00248	0.95	0.05	0.25

Power of 3-yr study comparing FluBlok v Comparators
Power to detect relative VE against 5 types of outcome events
By age group (or chronic disease status) and outcome
2-sided alpha=0.05 (likelihood ratio chi-sq test for superiority)
800,000 vaccinees expected per yr: 400K fluBlok v. 400K comparators

age=50-64 outcome=CVD hosp, Dec-March

row	N expectd 3 yrs FluBlok	N expectd 3 yrs Comprtr	proportion of comparators who have the outcome	RR = 1 minus relative VE	Relative VE: % of breakthru cases prevented	Power (prob. of rejecting Ho if rel_VE is true)
43	519,699	519,699	0.00620	0.70	0.30	>.99
44	519,699	519,699	0.00620	0.75	0.25	>.99

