We will also be monitoring the balance of potential confounders that may be related to influenza and to PCR testing in order to confirm that we are achieving the balance intended by our quasi-randomized shipment of vaccines to clinics. Once vaccinations begin, we will monitor on a weekly basis the balance of Flublok vaccinees versus SD-IIV vaccinees with respect to facility,

sex, and age group (18–49 years and 50–64 years). Additional demographic variables such as race and ethnicity may also be monitored. We will also monitor balance with respect to comorbidities such as chronic obstructive pulmonary disease (COPD), asthma, and diabetes. If we find that any facility is using Flublok or SD-IIV more (or less) than needed to achieve balance, we will work with the influenza program manager to adjust what is being administered.

By design, inpatient facilities did not participate in the quasi-randomization of influenza vaccine administration. We will therefore exclude patients who received Flublok or SD-IIV during an inpatient stay as these may be higher risk. Facilities that used only Flublok or only SD-IIV will also be excluded from the analysis.

In preparing our dataset for analysis, we will assess the balance in several ways to determine if the imbalance is substantially more than what we would expect to see. Despite our efforts, we anticipate that there will still be imbalances. We will create a facility-specific propensity score for each vaccinee, scoring their probability of receiving Flublok versus SD-IIV as a function of covariates, including but not limited to age, sex, race, ethnicity, comorbidity scores, influenza vaccination, and prior healthcare utilization history. Our Cox regression will be adjusted for the propensity score.

For PCR-confirmed outcomes, we plan to assess the outcomes that occur ≥ 14 days after vaccination up through to the end of each influenza season (as determined by KPNC, which is generally when the proportion of influenza-positive PCR tests drops below 10%) or the first week of May, whichever is later. For outcomes that are not tied to PCR-confirmation, the outcome or diagnosis must occur on or after the first day that KPNC begins use of the Cepheid GeneXpert PCR assay for the influenza season (generally the first Tuesday of October), but must begin no later than 14 days after the last day of the influenza season, as determined by KPNC.

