It is possible that patients enter, exit, and re-enter the KPNC population during the study period. Only patients who are members at the time of vaccination will be included in the analysis in order to most accurately ascertain the vaccine received. If additional exclusions need to be made based on membership, we will make the most appropriate determination for how to handle such cases at the analysis stage, but we anticipate that this would be a very small number of patients. Missing data will not be imputed.

For outcomes not based on PCR-confirmed influenza (e.g., hospitalized pneumonia and cardio-respiratory events), we will include in the analysis all such outcomes occurring within 14 days after the last day of the influenza season (as determined by KPNC) to account for influenza that may still be circulating after the “official” end of the season.

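### The SAP does not give the circulation-based follow-up rule that the protocol promised for hospitalised pneumonia and cardio-respiratory events, and its long, unreconciled season window pulls both secondary rVEs toward zero

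*SAP*

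**What the plan says.** Protocol 11.1 deals separately with outcomes that are not PCR-confirmed and names hospitalised pneumonia and cardio-respiratory events. For these it commits to an algorithm, to be described in the SAP, "to measure the intensity of influenza circulation to guide when to start and stop following for such events". Its example is that "hospitalized pneumonia during June when influenza is not circulating would not be included".

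The SAP's provisions are:

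- **Start (4.2 and 5.1.1.2).** The first day of seasonal use of the PCR assay, "generally the first Tuesday of October". This is a laboratory date and does not measure circulation.
- **Season end (4.2).** The point at which positivity "drops below 10%, or the first week of May, whichever is later".
- **Tail for community-acquired pneumonia (CAP) (4.2).** "The hospitalization for CAP must occur during the influenza season and no later than 14 days after the last day of the influenza season". The rule for cardio-respiratory events has the same form.
- **Restatement for non-PCR outcomes (5.1.1.2).** The event "must begin no later than 14 days after the last day of the influenza season, as determined by KPNC". A later paragraph says "we will include in the analysis all such outcomes occurring within 14 days after the last day of the influenza season", because influenza may still circulate after what it calls the official end. Neither sentence repeats the May floor.

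SAP 4.2 counts both endpoints whether or not a PCR test was taken. Both belong to the five secondary outcomes tested under Holm. The protocol's power rows for the nearest outcomes in ages 50-64 (Section 15) are labelled "age=50-64 outcome=PneumoniaHosp,Dec-March" and, for CVD hospitalisation, likewise December to March.

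**The concern.** Pneumonia, heart failure, infarction and stroke occur all year. The choice of influenza vaccine is not expected to affect admissions in weeks without influenza, so those events should have an rHR near 1. The Cox model forms risk sets by calendar day and gives one rHR, which is roughly an event-weighted average over the window. The more influenza-free weeks the window holds, the closer that rHR moves to 1.

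The protocol's circulation rule would limit this. The SAP has no circulation-based start. On the season definition in SAP 4.2, the 10% threshold can only lengthen the window. At stake are a real difference being missed in two Holm-tested secondaries, and a reader applying December-March powers to endpoints measured over a much longer period.

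**Working it through.** **1. Reproduce the stated power.** Inputs from Protocol Section 15: 519,699 per arm, comparator risk 0.00248 (pneumonia) or 0.00620 (CVD hospitalisation), rVE 10%, two-sided alpha 0.05.

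For pneumonia (row 41):
- e0 = 519,699 × 0.00248 = 1,289 events; e1 = 0.90 × 1,289 = 1,160.
- z = −ln(0.90) / √(1/1,289 + 1/1,160) = 0.1054 / 0.0405 = 2.60.
- Power = Φ(2.60 − 1.96) = 0.74, as stated.

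The same formula gives 0.98 for row 40 (rVE 15%) and 0.25 for row 42 (rVE 5%), both as stated. For row 47 (CVD hospitalisation, rVE 10%) it gives 0.984; a two-proportion calculation gives 0.985, which rounds to the stated 0.99.

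**2. Length of the window under SAP 4.2.** From the first Tuesday of October to 1-7 May, plus 14 days, both ends counted:

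| Season | Opens | Earliest close | Days | December-March |
|---|---|---|---|---|
| 2018-19 | 2 Oct | 15-21 May | 226-232 | 121 |
| 2019-20 | 1 Oct | 15-21 May | 228-234 | 122 |
| 2020-21 | 6 Oct | 15-21 May | 222-228 | 121 |

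December-March is 52% to 55% of these days. This is calendar time, not each person's follow-up: vaccination is still under way in October and November (Protocol 5.1.4 puts more than 75% of doses before Thanksgiving).

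**3. Dilution.** Let s be the share of comparator events outside circulation, with rHR = 1 there and rVE 10% inside. Assume that the December-March risks in the power table are the in-circulation risks.
- Pooled rVE = 10% × (1 − s).
- Comparator events = 519,699 × risk / (1 − s), which credits the extra events from the longer window.

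Example for pneumonia, s = 40%: pooled rVE 6.0%; e0 = 1,289/0.60 = 2,148; e1 = 0.94 × 2,148 = 2,019; z = 0.0619/0.0310 = 2.00; power 0.51.

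| s (assumed) | Pooled rVE | CAP power | CVD hospitalisation power | CAP power at alpha 0.01 (first Holm step) |
|---|---|---|---|---|
| 0 | 10% | 0.74 | 0.98 | 0.51 |
| 10% | 9.0% | 0.69 | 0.97 | 0.46 |
| 25% | 7.5% | 0.61 | 0.94 | 0.37 |
| 40% | 6.0% | 0.51 | 0.88 | 0.28 |
| 48% | 5.2% | 0.46 | 0.83 | 0.24 |

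The documents do not give s. The 48% row treats every day outside December-March as influenza-free, with a constant event rate and everyone at risk from early October, so it is an upper scenario. If on average half the cohort is at risk in October and November, and daily event rates outside December-March are 25% to 100% of the rate within it, December-March holds 86% to 60% of events. CAP power is then 0.67 to 0.52.

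**4. A season that contributes nothing.** With a circulation rule and two of three seasons contributing, e0 = 859 and e1 = 773, so z = 2.13 and CAP power is about 0.57. With the SAP 4.2 window, s = 40% and one season without circulation, pooled rVE is 10% × 0.60 × 2/3 = 4% and power is 0.26.

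**The case against.** **The May floor may not apply to these outcomes.** SAP 5.1.1.2 ties the cut-off for non-PCR outcomes to the last day of the season as KPNC determines it. It attaches the first week of May only to the sentence on PCR outcomes. On that reading falling positivity does close the window. This stands. A reader might infer that influenza activity can never shorten the window; that follows from the definition in 4.2 but not from the SAP as a whole. On either reading the start remains a laboratory date.

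**The SAP does have a circulation measure, and its window normally excludes June, the protocol's own example.** This also stands in part. The protocol, however, promised a rule for both start and stop, and the SAP gives none for the start.

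**The stated objectives are not limited to weeks of circulation.** Correct. Section 2.2 of both documents asks for rVE against these admissions without that limit. A reader might infer that the SAP endpoint no longer answers the objective; the documents do not support that. The departure is from the method in Protocol 11.1.

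**The size depends on the assumed share.** Correct. At s = 10% the loss is small, and power for CVD hospitalisation stays at 0.83 or above throughout. December-March is a power-table label, not a documented circulation period. The 0.26 in step 4 should be set against 0.57, not 0.74, because much of that fall comes from losing a season.

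**The SAP may examine rHR by time since season start and by single season.** These analyses are optional, and they do not change the estimate that is tested.

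**Conclusion.** The concern holds in this form. The SAP does not supply the circulation-based start and stop that Protocol 11.1 assigns to it, and its sections leave unclear whether the May floor applies to non-PCR outcomes. If SAP 4.2 is followed, the window is at least 222 to 234 days per season, nearly twice the period behind the stated powers, so those powers do not describe the SAP endpoints.

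The direction, toward zero for both secondary rVEs, is firm provided the vaccines do not differ in effect when influenza is absent. The size is not known: for 10% to 48% of events outside circulation, a 10% rVE reads as 9.0% to 5.2% and CAP power is 0.69 to 0.46. The figures for CVD hospitalisation only approximate the combined cardio-respiratory endpoint. The PCR-confirmed outcomes, including the primary, are not affected.

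**What to change.** In SAP 4.2 and 5.1.1.2:

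1. Reconcile the season end for non-PCR outcomes, saying whether the first week of May applies.
2. State the start and stop rule that the protocol promised. Base it on weekly positivity pooled over both vaccines, and fix it before any result by vaccine is seen. The SAP's existing 10% threshold is one option, though the SAP uses it only for season end and nothing in the documents supports it as a start rule. The December-March window already used for power is another.
3. Use that rule for the main CAP and cardio-respiratory analyses, and keep the October-to-May window as a sensitivity analysis.
4. Report the rHR in the low-circulation weeks as a negative-control period, where a value near 1 is expected.
5. Label the December-March powers as applying to that window only.

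The cost is SAP wording and one extra run on data already extracted. There will be fewer events, and some influenza-triggered admissions at the edges of the season move to the sensitivity analysis. A season with little circulation adds little or nothing; if one of three drops out, CAP power at a 10% rVE is about 0.57. The PCR outcomes need no change.
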